7.2.5 Early Termination Visit

The early termination visit is applicable for subjects withdrawing from the study prematurely. The site staff must go into IWRS to register the subject for early withdrawal.

The following data will be collected from subjects who are withdrawn before completing the study:

QoL questionnaire FAQLQ/FAIM forms ([Appendix 14.3](#)) will be completed by the subject (when applicable) and parent(s)/guardian(s) before any procedures at this visit are performed. The appropriate QoL questionnaire forms to complete depend on the age of the subject at the time of Visit 1.

A physical examination, including a complete skin examination, will be performed.

Vital signs (heart rate, systolic and diastolic blood pressure, and respiratory rate) for subjects in a sitting position will be measured.

Spirometry and PEF measurements (depending on the subject's age and ability to perform these tests) will be obtained.

SPT to cow's milk will be performed.

Blood samples for hematology and biochemistry laboratory tests, as well as immunological markers (IgE, IgG4) will be collected.

A urine pregnancy test will be performed for female subjects with childbearing potential.

Any AEs that have occurred since the previous visit will be documented and any changes in medications reported.

Examination, grading, and photography of the area of the skin used for Viaskin patch application will be performed.

Diary card will be collected.

The treatment box from the previous visit is collected from the subject (when applicable) and drug accountability/compliance will be assessed.

An EOS survey will be completed by the Investigator.

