7.3.1.4 Quality of Life Questionnaire Forms

The QoL questionnaire FAQLQ/FAIM forms²³ was to be completed by the subjects (when applicable, depending on age) and parents/guardians at Screening Visit 1, at Month 12 and Month 24, and at Month 36 and Month 48 for subjects who entered the study extension ([Table 2](#), [Table 3](#), [Table 4](#), and [Table 5](#)). The QoL questionnaire will be completed at the time of the switch and after 6, 12, 18 and 24 months of treatment with Viaskin Milk 300 µg ([Table 6](#) and [Table 7](#)). At these visits, the QoL forms must be completed by the subjects (depending on the subject's age at the time of Visit 1) and parents/guardians before any other study procedures are performed on that day.

The appropriate QoL questionnaire forms to complete depend on the age of the subject at Visit 1, as follows:

- Subjects 8 to 12 years old at the time of Visit 1 will complete the form FAQLQ-CF (Child Form) at Screening (Visit 1) and at Month 12 and Month 24, and at Month 36 and Month 48 for subjects who entered the study extension. Subjects who are 7 years old at the time of Visit 1 may also complete the form FAQLQ-CF at Screening (Visit 1), if their parent(s)/guardians(s) consider they are able to complete these questionnaires, so that when they turn 8 years old at Month 12, they will have a baseline questionnaire available. However, this is not mandatory.
- Subjects 13 to 17 years old at the time of Visit 1 will complete the form FAQLQ-TF (Teenager Form) at Visit 1 and at Month 12 and Month 24, and at Month 36 and Month 48 for subjects who entered the study extension.
- Parents/guardians of subjects 0 to 12 years old at the time of Visit 1 will complete the form FAQLQ-PF at Visit 1 and at Month 12 and Month 24, and at Month 36 and Month 48 for subjects who entered the study extension.
- Parents/guardians of subjects 13 to 17 years old at the time of Visit 1 will complete the form FAQLQ-PFT at Visit 1 and at Months 12 and 24 and at Month 36 and Month 48 for subjects who entered the study extension.

The FAIM is included as a part of the questionnaires listed above. The QoL questionnaire forms are included in [Appendix 14.3](#).

Data collected in the QoL forms must be entered on the appropriate pages of the eCRF. In order to maintain an unbiased assessment, the Investigator or study site

personnel must not influence the subject and/or parent(s)/guardian(s) while they are completing the forms.

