6 GENERAL ASPECTS FOR STATISTICAL ANALYSIS

6.1 GENERAL METHODS

6.1.1 General

All analyses and summaries will be produced using CCI [REDACTED]

Unless otherwise specified, summaries will be presented overall and for each age group, in total and by treatment (placebo/dose level/overall active). "Overall active" is a synonym for "All Doses Viaskin Milk". In the OL-period(s) analyses, it is defined as the subjects who were randomized / treated in one of the 3 Viaskin Milk doses for the double-blind treatment period.

The secondary and explorative efficacy endpoints, referring to "Change to Baseline" are all analyzed with respect to "Month 0". If not specified otherwise, summaries for changes from baseline indicate summaries relative to "Month 0" as well as relative to "Month 12", see [section 6.2.1](#) for definition.

Unscheduled assessments will not be included in summary tables unless specified otherwise, but will be included in the subject listings.

In case of repeated measurements in the scheduled time-windows, the first measurement will be used for analysis, if not specified otherwise.

Early termination assessments will be analyzed as having occurred at the next scheduled assessment.

All tables, listings and figures will include footers that identify the name of the program that created the item, together with the date and time on which it was created. Headers will include the total number of pages that the presentation contains and, for each page, the number of the page within the presentation.

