6.4 VISIT WINDOWS

Visit windows are defined in [section 7.4 of the study protocol version 6.0](#).

Out-of-window visits will be identified, discussed and classified as major or minor protocol violation in the data review meetings (DRMs). The first DRM was blinded and took place after the last randomized subject rolled over in the OL-phase or discontinued, but before database-lock of the 12-months period. Concomitant medications that started in the randomized blinded treatment period and are ongoing or still present in the open-label treatment period will be assigned to both periods.

Adverse Events that started in the randomized blinded treatment period and are ongoing or still present in the open-label treatment period will only be assigned to the period during which they appeared or worsened.

The following time windows during the DB-period are defined for each of the following visits:

Table 3: Time window definition

Visit	Timepoint (authorized window in study protocol)	Target Day	Lower bound	Upper bound
Visit 4	Day 1	1	First patch application	
Visit 5	Day 2	2	2	2
Visit 6	Day 8/ Week 1 (+/- 2 days)	8	3	14
Visit 7	Day 22/ Week 3 (+/- 3 days)	22	15	29
Visit 8	Week 6 (+/- 3 days)	43	30	60
Visit 9	Month 3 (+/- 7 days)	91	61	136
Visit 10	Month 6 (+/- 7 days)	182	137	227
Visit 11	Month 9 (+/- 7 days)	274	228	319
Visit 12	Month 12 (+/-7 days)	365	320	456

At each visit, the number and percentage of subjects respecting the time window defined in Table 3 will be provided.

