6.7 METHODS FOR WITHDRAWALS

Subjects who withdraw from the study prematurely will have all data listed and, where relevant, included in any summaries allocated to the next scheduled assessment.

7 DISPOSITION, PROTOCOL DEVIATIONS, DEMOGRAPHIC, OTHER BASELINE CHARACTERISTICS AND MEDICATION

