8.2 SECONDARY EFFICACY ENDPOINTS AND ANALYSES

ITT, OLS-500 or OLS-300 (if applicable) will be employed for secondary efficacy analyses. Observed data will be used, no imputation of missing data will be performed.

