8.2.6 Quality of Life Assessments

8.2.6.1 Food Allergy Quality of Life Questionnaires (FAQLQ)

8.2.6.1.1 General

This document is confidential

Statistical Analysis Plan

FAQLQs will be completed by study subjects 8 years old and older (FAQLQ-Child Form (FAQLQ-CF) for age range 8 to 12 years old, FAQLQ-Teenager Form (FAQLQ-TF) for age range 13 to 17 years old). Subjects who are 7 years old at the time of Visit 1 may also complete the form FAQLQ-CF at Screening (Visit 1), if their parent(s)/guardians(s) consider they are able to complete these questionnaires, so that when they turn 8 years old at Month 12, they will have a baseline questionnaire available. However, this is not mandatory.

Parents will also complete a FAQLQ questionnaire for subjects 0 to 12 years old (FAQLQ-Parent Form (FAQLQ-PF)) and for subjects 13 to 17 years old (FAQLQ-Parent Form Teenagers (FAQLQ-PFT)).

The FAQLQ forms will be completed at baseline, Months 12, 24, 36 or 48 and every 6 months during the Viaskin Milk open-label 300 μ g. The same questionnaire will be completed throughout the study according to the subject's age at Visit 1.

For the specific questionnaires the following sub-scores as defined in the respective scoring sheets - also available on www.faqlq.com - will be derived:

FAQLQ-CF (8-12 yrs) will be analyzed according to the 4 following domains [3]:

- EI: Emotional impact (Q no: 19-24),
- AA: Allergen avoidance (Q no: 4, 6-10, 15),
- RAE: Risk of accidental exposure (Q no: 11, 13-14, 16-17),
- DR: Dietary restrictions (Q no: 1-3, 5, 12, 18).

FAQLQ-PF (0-12 yrs) will be analyzed according to the 3 following domains [4]:

- EI: Emotional impact (Q no: 2, 6-7, 9-11, 23-28, 30),
- FA: Food-related anxiety (Q no: 1, 4-5, 16-17, 20-21, 29),
- SDL: Social and dietary limitations (Q no: 3, 8, 12-15, 18-19, 22).

The scores are calculated taking the reduced numbers of items for younger children into account: For children between 0-3 years old questions numbers 15 and higher are not applicable and for children aged between 4 and 6 years questions 27 to 30 are not applicable. Age at Visit 1 will be used to define which questions will be applicable during the study for each patient. Questions not needed will be not used for analysis.

These sub-scores rely on different numbers of items according to these age-groups (0-3, 4-6 and 7-12 years old).

FAQLQ-TF (13-17 yrs) will be analyzed according to the 3 following domains [5]:

- EI: Emotional impact (Q no: 5, 12, 19-23),

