12.4 AMENDMENT 4: FINAL VERSION 4.0, 18 DECEMBER 2017

Following changes from analyses scheduled in protocol amendment 4, dated 18 December 2017 have been implemented in this Statistical Analysis Plan (version 3.0):

- a) *In order to homogenize analyses strategy with DBV Technologies' other statistical analysis plans, early termination assessments will be analyzed as having occurred at the next scheduled assessment.*
- b) *Visit time windows have been defined for the main visits occurring during the randomized blinded treatment period. Number and percentage of subjects respecting the time window defined in Table 3 will be provided.*
- c) *Clarification has been provided in case of several filaggrin mutations presented by subject in order to define the subject's homozygous/heterozygous status.*
- d) *In order to homogenize analyses strategy with DBV Technologies' other statistical analysis plans, sensitivity analysis on primary endpoint presenting relative risks has been removed and replaced by presenting difference of responder rate and its Newcombe 95% confidence interval stratified on age group.*
- e) *Sensitivity analyses on primary endpoint have been added:*
 - *On missing data handling: analysis using observed data, analysis of best case scenario and of worst case scenario*
 - *On covariates: analyses adjusted on recruitment part of the study (Part A / Part B)*
- f) *Sensitivity analyses on cumulative reactive dose using an appropriate non-parametric test procedure. The treatment effect will be estimated using Hodges-Lehmann estimate of the difference in medians of CRD change from month 0. The corresponding 95% confidence interval and the p-value from the hypothesis test of no difference between the treatment groups (Wilcoxon rank-sum test) stratified on age group will be presented.*
- g) *In order to comply with requests from FDA on another project, serious adverse events occurring during DBPCFC will not be considered for adverse events analyses; they will be described separately.*

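### Early-termination values are analysed at the next scheduled assessment with no day limit, so QoL, SPT and immunology values taken well before Month 12 can enter the Month 12 secondary analyses

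*SAP*

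**What the plan says.** **The rule.** SAP 6.1.1: "Early termination assessments will be analyzed as having occurred at the next scheduled assessment". SAP 6.7 says that withdrawn subjects' data are listed and, "where relevant, included in any summaries allocated to the next scheduled assessment". SAP 12.4(a) records it as a change from protocol amendment 4, made to align with the sponsor's other plans: "early termination assessments will be analyzed as having occurred at the next scheduled assessment". No section gives a day limit or a minimum time on treatment.

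**What is collected.** Protocol 7.2.5: "The following data will be collected from subjects who are withdrawn before completing the study". The list includes FAQLQ/FAIM, SPT and immunological markers, whatever the day of withdrawal. It includes no food challenge.

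**When these measures are scheduled.** Protocol 7.3.1.4 places QoL "at Screening Visit 1, at Month 12 and Month 24", with later annual forms in the extension. SAP 8.2.6.1.1 agrees: "The FAQLQ forms will be completed at baseline, Months 12, 24, 36 or 48 and every 6 months during the Viaskin Milk open-label" 300 µg period. Under Protocol 7.2.2, blinded-year SPT after baseline falls at Months 3, 6 and 12, and immunology at Week 3 and Months 3, 6 and 12.

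**Where the values are used.** Change in QoL at Month 12 is tested by ANCOVA (SAP 8.2.6.1.2). Immunology and SPT go into repeated-measures models up to Month 12 (8.2.3.1, 8.2.4.1), as do the exploratory sIgE markers (10.3.2).

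**Other text on the same question.** SAP 6.2.1 defines Month 12 as the latest assessment at Visit 12 or 13. SAP 6.4 says: "The following time windows during the DB-period are defined for each of the following visits", and Table 3 then gives Visit 12 a target of day 365 with bounds 320 to 456. SAP 8.2 says: "Observed data will be used, no imputation of missing data will be performed".

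**The concern.** The label attached to an early-termination value depends on how sparse the schedule is, not on when the value was taken. For QoL the next scheduled form after any blinded-year withdrawal is Month 12, so a form completed in week 3 and one completed in month 11 carry the same label. SPT and immunology have the same problem on a smaller scale after Month 6.

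If the treatment effect builds up over the year, such values would pull the Month 12 contrasts towards no difference. If the number or timing of withdrawals differs between arms, the contrasts would also reflect who left and when. The SAP has other text that points towards a stricter Month 12 and does not say which text governs, so two programmers could build different Month 12 datasets.

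**Working it through.** The plan has no figure to reproduce here; the sample-size sections are redacted and not needed. The check applies the rule to the schedule and compares study days with Table 3.

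**Inputs.** Table 3 target days: Visit 7 = 22, Visit 9 = 91, Visit 10 = 182, Visit 11 = 274, Visit 12 = 365. Table 3 windows: Visit 7 days 15–29, Visit 8 days 30–60, Visit 10 days 137–227, Visit 11 days 228–319, Visit 12 days 320–456. Schedules as given above.

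**QoL.** The next scheduled assessment is always Visit 12.
- Largest shift: 365 − 1 = 364 days.
- Form completed after two weeks (day 15): 365 − 15 = 350 days, which is 320 − 15 = 305 days before the Table 3 lower bound. Table 3 would place it in the Visit 7 window, where no QoL is scheduled.

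**SPT and immunology.** After Month 6 the next scheduled assessment is Visit 12.
- Largest shift: 365 − 182 = 183 days.
- Value at day 190: 365 − 190 = 175 days, although day 190 lies in the Visit 10 (Month 6) window.
- Value at day 274: 365 − 274 = 91 days. It lies in the Visit 11 window, where neither measure is scheduled.

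**300 µg period.** QoL, SPT and immunology are collected every six months (Protocol 7.2.3), so the largest shift is about six months. Table 3 covers only the blinded period, so there are no analysis windows here.

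**Scale, as illustration only.** The readable text gives no early-termination rate. Let *f* be the share of Month 12 values that are early forms, and *g* the fraction of the full effect they carry. The estimated difference becomes 1 − *f*(1 − *g*) of its full value. Assume 80% power at full effect, two-sided 5%, normal approximation. With *g* = 0, power is Φ(2.80(1 − *f*) − 1.96) if the early forms are included and Φ(2.80√(1 − *f*) − 1.96) if they are left out. These were run with 49 per arm, but the arm size cancels once 80% is fixed.

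| Assumed *f* | Effect kept, *g* = 0 | Effect kept, *g* = 0.5 | Power, included (*g* = 0) | Power, left out |
|---|---|---|---|---|
| 5% | 95% | 97.5% | 76% | 78% |
| 10% | 90% | 95% | 71% | 76% |
| 20% | 80% | 90% | 61% | 71% |

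**The case against.** - **Month 12 is already defined.** SAP 6.2.1 ties it to Visit 12 or 13, and 6.7 limits inclusion to where it is relevant. On that reading a day-15 form is not a Month 12 value. The phrase in 6.1.1 could also mean the next visit rather than the next assessment of that measure, which would leave the form in no QoL table. These readings are possible, but nothing says that they override 6.1.1, and the text speaks of an assessment. The ambiguity itself needs resolving.
- **The rule was chosen deliberately**, for consistency with other plans. That explains it but does not answer the timing problem.
- **Leaving early values out has its own cost.** For QoL, with a single blinded-year post-baseline time point, it leaves mostly completers, which also depends on who withdrew. This stands, and is a reason to offer the windowed analysis as a sensitivity analysis. It weighs less for SPT and immunology, where the repeated-measures model keeps a subject's earlier visits.
- **Loss of effect is assumed, not shown.** This also stands: no document gives the number, timing or content of early-termination values.
- **The blinded-year models have been run and reported** (SAP 11.1), and they are not repeated for open-label time points. The remaining 300 µg summaries are descriptive. This limits what can be changed prospectively.

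**Conclusion.** The point holds as a weakness of a stated rule in secondary and exploratory analyses. On the natural reading of 6.1.1, blinded-year early-termination QoL forms can be moved by up to about 364 days, and SPT or immunology values taken after Month 6 by up to about 183 days, into Month 12 analyses. The SAP does not reconcile this with 6.2.1, Table 3 or 8.2. The effect on the results cannot be sized; the table above rests on assumed rates and assumed loss of effect.

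A reader might infer three stronger claims that the documents do not support:
- **That the rule contradicts Table 3.** The only stated use of those windows is to count subjects who fall within them; they are not said to allocate analysis values.
- **That the rule breaks the ban on imputation in 8.2.** An early-termination value is observed and relabelled; nothing missing is filled in. The tension is with the spirit of an observed-data analysis.
- **That the primary result is affected.** The early-termination visit has no food challenge, and a missing Month 12 response counts as non-response (SAP 8.1.1). Cumulative reactive dose and challenge severity are unaffected for the same reason.

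**What to change.** Replace the rule in SAP 6.1.1 and 6.7 with assignment by actual study day. Use an early-termination value at a time point only if all three conditions hold:
1. It falls in that visit's Table 3 window.
2. The measure is scheduled at that visit.
3. The subject has no scheduled value there.

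Otherwise list it only. A day-15 QoL form and a day-274 SPT value would then be listed. A day-190 SPT value would count as Month 6 only if the Month 6 value is missing, which agrees with the existing preference in 6.1.1 for the first measurement in a window. State that this rule and the 6.2.1 definition are to be read together.

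Apply it in two places:
- **Blinded year:** a sensitivity re-run of the reported Month 12 QoL, SPT and immunology models, labelled as post-unblinding, with the number of early-termination values reclassified in each arm.
- **300 µg period:** prospectively in the summaries, with windows split midway between the six-monthly visits, that is at Months 3, 9, 15 and 21 after the switch (for example (6 + 12)/2 = 9).

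The cost is SAP wording, one windowing step, slightly fewer Month 12 records, and a sensitivity analysis defined after unblinding.

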6.1.2 Presentation of Descriptive statistics

If not stated otherwise continuous variables will be summarized using the number of

This document is confidential

Statistical Analysis Plan

subjects with evaluable data (n), mean, standard deviation (SD), median, first and third quartiles (Q1, Q3), minimum and maximum. The same number of decimal places as in the raw data will be presented when reporting minimum, maximum and median. Values rounded to 1 more decimal place than in the raw data will be presented when reporting the mean, and values rounded to 2 more decimal places than in the raw data will be presented when reporting the SD.

Categorical variables will be summarized using the number of observations (n), frequency and percentage of subjects. All percentages will be presented as rounded to one-decimal point, unless otherwise specified. Percentages equal to 100 will be displayed as 100% and percentages will not be presented for zero frequencies.

Unless stated otherwise (e.g. in the respective footnotes), the percentages will be based on the number of non-missing observations (in the respective visit, if applicable). The column header will still contain the number of subjects in the treatment group.

There will be a row for the number of missing observations if there are missings available. The number of subjects on which the percentages rely on is given in the summaries explicitly, if it is different from the numbers given in the column headers. This is mainly applicable

- for the frequency counts with missing values (which will not be used in the calculations)
- for the visit-wise summaries (as the numbers of available subjects per visit might be different to the number of subjects in the respective population displayed in the column header).

6.1.3 Presentation of Statistical Tests

Unless otherwise stated, all formal tests of hypotheses will be conducted at the two-sided level of significance with alpha=0.05.

Any calculated p-values will be rounded to 3 decimal places; p-values less than 0.001 will be presented as 'p < 0.001' and p-values greater than 0.999 will be presented as 'p > 0.999'.

6.1.4 Presentation of Listings

All relevant subject data will be included in listings and sorted by dose level at the beginning of treatment, subject's number and visit, as applicable, for all randomized subjects. Subject data will be assigned to randomized blinded vs. open-label or the different periods (Screening, 1-DB, OL500, 1-SW, 2-SW, and Follow-Up), if applicable.

Data from Part A Cohorts 1, 2, and 3 will be clearly identified.

Statistical Analysis Plan

6.2 KEY DEFINITIONS

6.2.1 Baseline, Month 0, Month 12, LV-OL-500 and last value prior to active treatment

“Month 0” is defined as the latest available assessment (scheduled or unscheduled) before first application of any Viaskin patch, whether this patch is active or placebo. Except for efficacy endpoint using information collected during screening DBPCFC, assessments derived throughout the DBPCFC at Screening (vital signs...) will not be considered.

“Baseline” is identical to “Month 0”. The later will be used in the statistical outputs for clarification and precision, as the term “Baseline” used in the protocol will sometimes refer to a specific Visit.

“Month 12” is defined as the latest available assessment at Visit 12 or Visit 13 before first application of any Open-Label Viaskin patch, without using the assessments derived throughout any DBPCFC.

“LV-OL-500”: The last value during Viaskin Milk 500µg Open-Label treatment period is defined as the latest available assessment (scheduled or unscheduled) during the Viaskin Milk 500µg OL period (OL-500), i.e the one collected during switch to Viaskin Milk 300µg visit (VS1), or during early termination visit, or during any visit earlier (except for the one used to define Month12), whichever is the latest. LV-OL-500 will serve as a baseline value for the OL-300 analyses labelled as “last value prior to switch to Viaskin Milk 300µg” for subjects in OLS-300.

Last value prior to active treatment is equivalent to Month 0 for subjects initially randomized to an active treatment group and Month 12 for subjects initially randomized to placebo.

